### 5.3 AEs coding/grading

Adverse events are coded using the Medical dictionary for regulatory activities (MedDRA) terminology. AEs are assessed by investigators according to the most current Common Terminology Criteria for Adverse Events (CTCAE) version 4.0

### 5.4 Laboratory parameters derivations

Grade categorization of lab values will be assigned programmatically as per NCI Common Terminology Criteria for Adverse Events (CTCAE) version 4.0 (specify version used in the RAP). The calculation of CTCAE grades will be based on the observed laboratory values only, clinical assessments will not be taken into account. The criteria to assign CTCAE grades are given in Novartis internal criteria for CTCAE grading of laboratory parameters. The latest available version of the document based on the underlying CTCAE version 4.0 at the time of analysis will be used.

A severity grade of 0 will be assigned for all non-missing lab values not graded as 1 or higher. Grade 5 will not be used.

### 5.5 Statistical models

#### 5.5.1 Primary analysis

The primary analysis is detailed in [Section 2](#).

SAS procedure FREQ with EXACT statement for one-way tables will be used to estimate the proportion of patients (binary outcome = 1 or “Yes”), along with the associated 95% ( $=100 \times (1 - \text{two-sided } \alpha \text{ level})$ ) two-sided Clopper- Pearson CI [[Clopper and Pearson 1934](#)]. SAS procedure FREQ with EXACT statement for two-way tables will be used to perform the Fisher exact test.

#### 5.5.2 Key secondary analysis

NA.

#### 5.5.3 Other secondary/██████████ analysis

##### Kaplan-Meier estimates

An estimate of the survival function in each treatment group will be constructed using Kaplan-Meier (product-limit) method as implemented in PROC LIFETEST with METHOD=KM option. The PROC LIFETEST statement will use the option CONFTYPE=LOGLOG.

Median survival for each treatment group will be obtained along with 95% confidence intervals calculated from PROC LIFETEST output using the method of [[Brookmeyer and Crowley 1982](#)]. Kaplan-Meier estimates of the survival function with 95% confidence intervals at specific time points will be summarized. The standard error of the Kaplan-Meier estimate will be calculated using Greenwood’s formula [[Collett 1994](#)].

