#### 2.7.2.1.1 Analysis of PCR-corrected ACPR using Kaplan-Meier method

For the FAS, the proportion of patients with PCR-corrected ACPR at Day 29 and 95% CI will be also estimated using the Kaplan-Meier method ([Stepniewska and White 2006](#) and [WHO 2015](#))

**Event** = PCR-corrected non-responder during the study (same as at Day 29, See Section 2.1). The event time is the first time when the patient becomes a non-responder based on PCR-correction. If a patient parasite is not cleared at all, Day 7 is considered as the event time.

The PCR-corrected responder rate at Day 29 is estimated by the survivor function at Day 29 using the Kaplan-Meier method.

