### **2.7.2.4 Recrudescence**

Recrudescence is defined as appearance of asexual parasites after clearance of initial infection with a genotype identical to that of parasites present at baseline. Recrudescence must be confirmed by PCR analysis.

Incidence rates of recrudescence at Study Day 29 will be estimated by Kaplan-Meier method based on the subset of FAS patients who have clearance of initial infection before Day 15. Time to recrudescence will be calculated from the time of first study medication to the date of first event if a patient experiences the event and be censored at the time of last parasite

assessment if a patient does not experience the event. Patients who experienced a new infection will be censored at the first time of new infection.

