### **2.7.2.5 Time to event analysis for reinfection**

Reinfection is defined as appearance of asexual parasites after clearance of initial infection with a genotype different from those parasites present at baseline. Reinfection must be confirmed by PCR analysis.

Incidence rates of reinfection at Day 29 will be estimated by the Kaplan-Meier method based on the subset of FAS patients who have clearance of initial infection before Day 15.

Time to event (reinfection) will be calculated from the time of first study medication to the date of first event if a patient experiences the event and will be censored at the time of last parasite assessment if a patient does not experience the event. Patients who experienced recrudescence will be censored at the first time of recrudescence.

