**Table 2-4 Overview of analysis methods for baseline data and efficacy variables**

Variable(s)	Summary statistics for binary/ categorical data	Listings	95% CI for each treatment group	Summary statistics for continuous data	Time-to-event data analysis K-M	Graphs
Medical history	X	X	-	-	-	-
Demographics and baseline characteristics	X	X	-	X	-	-
Patient disposition	X	X	-	-	-	-
Prior medication use	X	X	-	-	-	-
Concomitant medication use	X	X	-	-	-	-
Concomitant rescue medication use	X	X	-	-	-	-
Non-study drug antimalarial medication use	X	X	-	-	-	-
Prior other prohibited medications use	X	X	-	-	-	-
Concomitant other prohibited medications use	X	X	-	-	-	-
PCR-corrected ACPR response at Days 15 and 29	X	X	X	-	-	-
PCR -uncorrected ACPR response at Days 15 and 29	X	X	X	-	-	-
Proportion of patients with parasitaemia at 12, 24, and 48 hours after treatment;	X	X	X	-	-	-
Time to parasite clearance (PCT)	-	X	-	-	X	X
Time to fever clearance (FCT)	-	X	-	-	X	X
Proportion of patients with early treatment failure	X	X	X	-	-	-
Proportion of patients with late clinical failure	X	X	X	-	-	-
Proportion of patients with late parasitological failure (LPF)	X	X	X	-	-	-

Variable(s)	Summary statistics for binary/categorical data	Listings	95% CI for each treatment group	Summary statistics for continuous data	Time-to-event data analysis K-M	Graphs
Incidence rate of recrudescence at Days 29.	X	-	-	-	X	X
Incidence rate of reinfection at Days 29	X	-	-	-	X	X

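### The only Kaplan-Meier interval the SAP names (Greenwood, log-log) is undefined in an arm with no event, and Day 29 recrudescence and reinfection have no other interval

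*SAP*

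**What the plan says.** SAP 5.5.3 sets one method for all Kaplan-Meier work. "Kaplan-Meier estimates of the survival function with 95% confidence intervals at specific time points will be summarized". Greenwood's formula supplies the standard error, and "The PROC LIFETEST statement will use the option CONFTYPE=LOGLOG". No rule covers an arm in which nobody, or everybody, has the event.

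Three sets of Day 29 results depend on this method:

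- **Recrudescence (SAP 2.7.2.4).** "Incidence rates of recrudescence at Study Day 29 will be estimated by Kaplan-Meier method based on the subset of FAS patients" whose initial infection cleared before Day 15. It is the endpoint of a separate secondary objective (Protocol Table 2-1, SAP Table 1-2).
- **Reinfection (SAP 2.7.2.5).** "Incidence rates of reinfection at Day 29 will be estimated by the Kaplan-Meier method based on the subset of FAS patients", with the same clearance condition.
- **ACPR (SAP 2.7.2.1.1 and 2.7.2.1.2).** For the FAS, "the proportion of patients with PCR-corrected ACPR at Day 29 and 95% CI will be also estimated using the Kaplan-Meier method"; uncorrected ACPR is treated the same way. This comes on top of the crude ACPR rate, which has an exact Clopper-Pearson interval by arm and cohort (SAP 2.7.2.1).

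In SAP Table 2-4 the row "Incidence rate of recrudescence at Days 29" has a mark for categorical summaries and for Kaplan-Meier, and a dash under the column for a 95% CI per treatment group. The reinfection row is the same.

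**The concern.** The log-log interval works on the scale log(-log S). At S = 1 that value does not exist and Greenwood's variance is zero, so there is nothing to back-transform. An analyst who follows 5.5.3 to the letter has no valid interval for an arm with no recrudescence or no reinfection.

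The failure falls on the arms with the best observed result. The SAP plans no statistical comparison with Coartem for efficacy (SAP 2.7), so an interval is the main protection against over-reading an observed 0% in a small arm. Zero out of 10 and zero out of 60 are very different strengths of evidence, and a valid interval would show it. The SAP also points two ways on whether these endpoints get an interval: 5.5.3 speaks generally of 95% intervals at time points, while Table 2-4 marks none for them.

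**Working it through.** **Inputs**

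- Transform and standard error: log-log and Greenwood (SAP 5.5.3).
- KAE609 arm sizes (SAP 1.1, Protocol Table 5-1): three arms of 10 (Cohorts 1 and 2) and six arms of 20 (Cohorts 3 to 6).
- Coartem: 60 over six cohorts (SAP 3.2), so 10 per cohort.
- Check of total: 3 × 10 + 6 × 20 + 6 × 10 = 210, the planned number in the protocol.
- Earlier data (Protocol 3.6): recrudescence in 4 patients, printed as 36%. 4/11 = 36%. With the 25 patients that Protocol 9.8 lists for the 10 to 30 mg study it would be 4/25 = 16%. Both are used as a range.
- Expected event rates for this trial's arms: none stated. All rates below are assumptions.

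**Check against the plan's own figures.** The documents give no figure for the Kaplan-Meier interval. As a check on the arm sizes and the binomial model, exact enumeration of the two-sided Fisher test at 5%, 40% against 5%, gives 76.7% and 91.3% (10 and 20 KAE609 against 40 Coartem) and 76.0% and 94.2% (against 60). SAP 3.2 states 77%, 91%, 76% and 94%.

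**Interval without censoring.** With d events in n patients, S = 1 - d/n, SE = sqrt(S(1-S)/n), and the limits are S^exp(±1.96·SE/(S·|ln S|)).

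- d = 0: S = 1, SE = 0, ln S = 0. The exponent is 0/0 and log(-log 1) is undefined.
- d = n: S = 0 and ln S does not exist, so the interval is again undefined.
- d = 1, n = 10: S = 90%, limits 47.3% to 98.5%.
- d = 1, n = 20: S = 95%, limits 69.5% to 99.3%.

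A single event is therefore enough for the method to work. The problem is confined to the two extremes.

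**Exact limit with no event.** The Clopper-Pearson upper limit for the event rate is 1 - 0.025^(1/n): 30.8% for 0/10, 16.8% for 0/20 and 6.0% for 0/60. The clearance condition can make the subset smaller: 36.9% for 0/8 and 18.5% for 0/18.

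**How often an arm has no event.** For one arm, P(no event) = (1-p)^n. For at least one of the nine KAE609 arms it is 1 - [1-(1-p)^10]^3 · [1-(1-p)^20]^6. For at least one of the six Coartem arms it is 1 - [1-(1-p)^10]^6. A common rate p is assumed within each set of arms, with no censoring.

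| True rate p | One arm, n=10 | One arm, n=20 | Any of 9 KAE609 arms | Any of 6 Coartem arms |
|---|---|---|---|---|
| 5% | 60% | 36% | 99.5% | 99.6% |
| 10% | 35% | 12% | 87% | 92% |
| 16% | 17% | 3% | 53% | 68% |
| 36% | 1.2% | 0.01% | 3.5% | 6.7% |

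Example, KAE609 at 5%: 1 - (1-0.5987)^3 × (1-0.3585)^6 = 1 - 0.0646 × 0.0697 = 0.9955 (0.99550 to five places).

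For a single arm, no event is more likely than not only if p < 1 - 0.5^(1/n), which is 6.7% for n = 10 and 3.4% for n = 20.

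**The case against.** The strongest reply is that little depends on this, and much of it stands.

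- **Zero events is not the expected result in a given arm.** A reader might infer that zero events is what most arms of 10 to 20 will show. The documents do not support that. It needs true rates below 6.7% or 3.4%, and no such rate is stated for any arm. The doses in Cohorts 1 and 2, which are the KAE609 arms of 10, are described as sub-therapeutic. Earlier recrudescence is printed as 36%, and earlier early failure, an event in the Kaplan-Meier ACPR analysis, as 42% at 10 mg and 25% at 20 mg. At recrudescence of 16% to 36% a given arm has no event with probability 17% to 1.2% (n = 10) or 3% to 0.01% (n = 20). What remains is that at least one arm is likely to be affected if true rates are about 10% or lower.
- **Cure rates are not left without a valid interval.** Crude Day 15 and Day 29 ACPR, corrected and uncorrected, have Clopper-Pearson intervals. Only the additional Kaplan-Meier estimate is affected.
- **Recrudescence is partly visible elsewhere.** It makes a patient a PCR-corrected non-responder from Day 8, so the exact ACPR interval reflects it. Table 2-4 also plans categorical summaries, so counts would be shown. A reader might infer that 0/10 and 0/60 would look equally certain, but that goes too far: whether the software prints a blank or a zero-width interval cannot be settled from the documents. There would still be no interval specific to recrudescence or reinfection.
- **Table 2-4 may mean that no interval is intended.** That reading is possible, since 2.7.2.4 and 2.7.2.5 promise only estimated rates. It then conflicts with the general sentence in 5.5.3, and the secondary objective on recrudescence would be reported without any statement of precision.

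**Conclusion.** The point holds in a limited form. The only interval named for Kaplan-Meier estimates at time points is undefined when an arm has no event or only events, and no fallback is given. For Day 29 recrudescence and reinfection no other interval is planned, and Table 2-4 and 5.5.3 disagree on whether one is due.

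How often this happens depends entirely on rates that the documents do not state. On a common assumed rate without censoring, it reaches at least one KAE609 arm almost surely at 5% and about half the time at 16%, but rarely at 36%. Where it happens, the missing information is substantial: an observed 0% is compatible with a true rate of up to 30.8% in an arm of 10.

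The severity is minor. These endpoints are secondary and descriptive. The primary hepatic analysis uses Clopper-Pearson intervals and Fisher tests and does not depend on this method.

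**What to change.** In SAP 5.5.3, for the Day 29 Kaplan-Meier proportions (recrudescence, reinfection and the additional ACPR estimates), name an interval that is valid at 0 and 1. The beta product confidence procedure is one choice; without censoring it reduces to Clopper-Pearson. State that assessments in the Day 29 window, which SAP Table 5-6 opens at Day 26, are set to nominal Day 29. Otherwise patients last seen on Days 26 to 28 are censored before Day 29 and drop out of the risk set.

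At minimum, add one sentence: when no event occurs in an arm, report the Clopper-Pearson limit using the number of patients with an evaluable assessment in the Day 29 window. The number at risk on Day 29 itself should not be the denominator, for the reason just given.

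Bring Table 2-4 into line by marking a 95% CI for recrudescence and reinfection. The log-log interval can stay for parasite and fever clearance times.

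The cost is a short SAP change and a small program. The intervals will be slightly wider and conservative.

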## 5.6 Rule of exclusion criteria of analysis sets

**Table 5-9 Protocol deviations and non-PD criteria leading to exclusion from analysis sets**

Analysis Set	PD (Description and ID) that causes Subjects to be excluded	Non-PD criteria that cause Subjects to be excluded
Randomized	
 
Informed Consent for study participation not obtained and subject entered trial (INCL06)
 
	
 
Not randomized
 
Misrandomized if identified from IRT
 

FAS	NA	
 
Not in Randomized set;
 
Baseline parasitaemia count is 0 or missing
 
No study drug taken
 

PPS	
 
Parasite specie is other than Plasmodium falciparum OR mixed infection (EXCL01)
 
Baseline plasmodium falciparum parasite count <500/uL or >50000/uL at screening visit (INCL03)
 
No fever within the past 24 hours at baseline (INCL04)
 
Received non-study concomitant antimalarial drugs between Day 1 and Day 29 without experiencing treatment failure (COMD02)
 
Patients who received concomitant prohibited medication which found to change the exposure that impacts efficacy. (COMD01b)
 
	
 
Not in FAS;
 
<80% of randomized study medication taken
 
Not classified as non-responder before Day 8, no positive blood smear parasite on Day 8 onwards, and blood smear parasite result is missing at Day 29.
 
Not classified as non-responder before Day 8, have at least one positive blood smear parasite result between Day 8 and Day 29 which cannot be determined as recrudescence or new infection based on PCR genotyping;
 

SAF	NA	
 
Not in Randomized set;
 
No study drug taken
 

PK	Patients who received concomitant prohibited medication which found to change the exposure that impacts interaction in PK parameters (COMD01c)	
 
Not in SAF
 
No evaluable pharmacokinetic parameter data
 
<80% of randomized study medication taken
 

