9.1 Analysis sets

Randomized set

All patients who are randomized.

Full analysis set (FAS)

FAS will be comprised of all patients from Randomized set who take at least one dose of study treatment during the treatment period and whose baseline parasitaemia count is greater than 0. Following the intent-to-treat principle, patients will be analyzed according to the treatment group assigned to at randomization.

Safety set (SAF set)

Safety set includes all patients who take at least one dose of study drug during the treatment period. Patients will be analyzed according to treatment received. Full details will be described in the statistical analysis plan (SAP).

Per-protocol set (PPS)

PPS will be comprised of patients in FAS who

- did not have any important protocol deviations
- took at least 80% of assigned study medication(s). If a patient vomited the original dose but did not vomit the replacement dose, the patient is considered as taking the dose of study medication. Except for patients who are assigned to Coartem treatment, this requires that all patients take all KAE609 dosages as assigned

- did not take other antimalarial medications prior to Study Day 29 for reasons other than rescue medication given for *P. falciparum* related treatment failure, and
- met at least one of the following criteria: (a) classified as treatment failure before Study Day 8 (see [Section 6.5.8](#)), (b) absent from parasitaemia at Study Day 29, or (c) had valid PCR evaluations at baseline and at the time point with parasitaemia if parasitaemia is present at Study Day 8 or later.

Important protocol deviations for exclusion from PPS will be identified by the clinical team before the final database lock.

PK analysis set

All subjects in the safety analysis set who had evaluable PK parameter data and took at least 80% of assigned study medication.

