9.4 Analysis of the primary variable(s)

The primary variable is a safety related endpoint. Therefore, it will be analyzed primarily using the SAF set. Efficacy variables are related to secondary [REDACTED] and the related analyses will be presented in [Section 9.5](#) and [Section 9.6](#).

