## 2.2 Analysis sets

**Randomized set (RAN)** : All patients who are randomized and not misrandomized if identified from IRT and who did not experience any important protocol deviation related to informed consent.

**Full analysis set (FAS)** : FAS will be comprised of all patients from Randomized set who take at least one dose of study treatment during the treatment period and whose baseline parasitaemia count is greater than 0. Following the intent-to-treat principle, patients will be analyzed according to the treatment group assigned to at randomization.

**Safety set (SAF set)** : Safety set includes all patients who take at least one dose of study drug during the treatment period. Patients will be analyzed according to treatment received.

**Per-protocol set (PPS)** : PPS will be comprised of patients in FAS who

- did not have any important protocol deviations
- took at least 80% of assigned study medication(s). If a patient vomited the original dose but did not vomit the replacement dose, the patient is considered as taking the dose of study medication. Except for patients who are assigned to Coartem treatment, this requires that all patients take all KAE609 dosages as assigned. For Coartem, the patient needs to take at least 5 doses of study drug to have taken 80%.
- did not take other antimalarial medications prior to Study Day 29 for reasons other than rescue medication given for *P. falciparum* related treatment failure, and
- met at least one of the following criteria: (a) classified as treatment failure before Study Day 8 (see [Section 2.1.1.1](#)), (b) absent from parasitaemia at Study Day 29, or (c) had valid PCR evaluations at baseline and at the time point with parasitaemia if parasitaemia is present at Study Day 8 or later.

Important protocol deviations for exclusion from PPS are specified in Table 5-9 and all other important protocol deviations will be identified by the clinical team before the final database lock.

**PK analysis set :** All subjects in the safety analysis set who had evaluable PK parameter data and with at least 80% compliance to study medication and who did not experience any important protocol deviation as mentioned in Table 5-9.

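### SAP 2.2 keeps every dosed patient in the Safety set, but SAP Table 5-9 also removes dosed patients outside a narrowed Randomized set; the effect is unknown and may be nil

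*SAP*

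**What the plan says.** **Safety set (SAF).** SAP 2.2 states: "Safety set includes all patients who take at least one dose of study drug during the treatment period", with analysis by treatment received. A note in SAP 2.4.1 repeats that anyone dosed belongs to the set, whether or not the dose was vomited. Protocol 9.1 has the same dosing rule and adds: "Full details will be described in the statistical analysis plan (SAP"). The SAF row of SAP Table 5-9 gives two reasons for exclusion: "Not in Randomized set", and having taken no study drug.

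**Randomized set.** Protocol 9.1 has simply "All patients who are randomized". SAP 2.2 has "All patients who are randomized and not misrandomized if identified from IRT and who did not experience any important protocol deviation related to informed consent". The Randomized row of Table 5-9 lists "Misrandomized if identified from IRT" and a single coded consent deviation, "Informed Consent for study participation not obtained and subject entered trial (INCL06").

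**Use of the set.** Of the primary ALT/AST variable, protocol 9.4 says "it will be analyzed primarily using the SAF set", and SAP 2.5.2 runs the exact intervals and Fisher tests on it. The PK row of Table 5-9 excludes anyone outside SAF. SAP Table 2-6 lists Safety-set outputs for the safety review, including the liver enzyme tables.

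**The concern.** The SAP gives two membership rules for the set that carries its primary analysis. For most dosed patients they agree. They part for a dosed patient who falls outside the SAP's Randomized set, and nothing in the SAP limits those removals to undosed patients.

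The case that matters most is a patient who consented, was dosed, and was misrandomized. Under Table 5-9 as written, that patient's liver results would leave the primary analysis, the Safety-set outputs for the safety review and the PK set. A safety analysis by treatment received would normally keep such a patient, because an allocation error does not undo exposure. With 10 or 20 patients per KAE609 arm, one patient is visible in the reported rate.

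**Working it through.** **1. The two rules side by side**

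| Patient | SAF by SAP 2.2 and 2.4.1 | SAF by Table 5-9 |
|---|---|---|
| Dosed, consented, not misrandomized | in | in |
| Dosed, consented, misrandomized per IRT | in | out |
| Dosed, consent not obtained (INCL06) | in | out |
| Dosed, another important consent deviation (if any exists) | in | out if the Randomized set is read from SAP 2.2; in if read from Table 5-9 |
| Not dosed | out | out |

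The conflict sits in rows two to four. The documents give no count for any of them.

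**2. The plan's own power figures**

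Inputs from SAP 3.2 and protocol 9.8.2: true rates 40% (KAE609) and 5% (Coartem), 60 pooled Coartem patients, two-sided Fisher exact test at 5%. Stated power is 76% for n = 10 and 94% for n = 20.

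Power = Σx Σy b(x; n, 0.40) × b(y; 60, 0.05) × 1{Fisher p(x, y) ≤ 0.05}, where b is the binomial probability.

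- 10 vs 60: 76.0%. 20 vs 60: 94.2%. Both stated figures reproduce.
- One KAE609 patient fewer: 9 vs 60 gives 75.3%; 19 vs 60 gives 93.2%.

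Planned power falls by about one point or less.

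**3. Effect on a reported rate**

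Event counts here are assumed. The exact 95% limits are the Beta(x, n − x + 1) quantile at 0.025 and the Beta(x + 1, n − x) quantile at 0.975.

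| Before | One patient with an event lost | One patient without an event lost |
|---|---|---|
| 3/20 = 15.0% (3.2 to 37.9) | 2/19 = 10.5% (1.3 to 33.1) | 3/19 = 15.8% (3.4 to 39.6) |
| 2/10 = 20.0% (2.5 to 55.6) | 1/9 = 11.1% (0.3 to 48.2) | 2/9 = 22.2% (2.8 to 60.0) |

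Losing a patient with an event lowers the rate by 15.0 − 10.5 = 4.5 points (n = 20) or 20.0 − 11.1 = 8.9 points (n = 10). Every interval overlaps its counterpart widely.

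**4. Effect on the Fisher p-value, 3/20 to 2/19**

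| Assumed Coartem events | p before | p after |
|---|---|---|
| 0/60 | 0.014 | 0.056 |
| 1/60 | 0.046 | 0.142 |
| 2/60 | 0.097 | 0.243 |
| 3/60 | 0.162 | 0.589 |

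Among these counts, p crosses 0.05 only with 0 or 1 Coartem events.

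**The case against.** **Table 5-9 may simply be the operating rule.** It sits under a heading about exclusion rules, the SAP's document history says the set definitions were adapted to agree with it, and the protocol leaves full SAF details to the SAP. This makes a drafting omission in SAP 2.2 the likeliest explanation, and for SAF it rules out a charge of departing from the protocol. It does not settle membership: the current SAF sentence in SAP 2.2 carries no Randomized-set condition, and neither does SAP 2.4.1.

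**Nobody may be affected.** Study drug is released through the IRT after eligibility is confirmed (protocol 5.3 and 5.5.2), and protocol 5.3 and 5.5.1 foresee patients who are randomized but not treated. If *misrandomized* means that group, both rules exclude them anyway. This is plausible and stands as a limit on the point, but it is inference, because the term is undefined.

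**Stronger readings the documents do not support:**

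- A reader might infer two different consent rules. The wording differs, but INCL06 is the only consent deviation coded in Table 5-9 and may be the only important one. A real difference in scope is not shown.
- A reader might infer that the study's conclusion could turn on this. The crossings in step 4 need a dosed excluded patient who had the event, in an arm with exactly that count, and at most one Coartem event. The plan has no pre-defined hypothesis and weighs the results together with patient narratives (protocol 9.4.2, SAP 2.5.2), so crossing 0.05 has no decision role.
- A reader might infer that the interim suspension triggers are exposed. They run on data review reports and dosage records (protocol 9.7, SAP 2.15). Only the Safety-set outputs in Table 2-6 would be.

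**Conclusion.** The inconsistency is real and stands in the current SAP text. Followed as written, Table 5-9 would drop a dosed, consented but misrandomized patient from the primary hepatic-safety analysis, while SAP 2.2 would keep that patient.

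Severity is minor. The number affected is not given and may be zero. The rate shifts in step 3 rest on assumed event counts and on the loss of one dosed patient; they show scale and predict nothing. The SAP's narrowing of the Randomized set relative to the protocol is stated openly. Its absence from SAP Section 4, which reads NA, is a matter of record-keeping.

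**What to change.** Reconcile the two passages so that misrandomization alone never removes a dosed patient from SAF: delete the Randomized-set condition from the SAF row of Table 5-9. The PK set then follows, because its row refers to SAF.

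If patients without informed consent have to be excluded, name INCL06 in the SAF row as the only exclusion besides taking no study drug, put the same words in the SAF sentence of SAP 2.2, and report the number of dosed patients it removes.

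Worthwhile housekeeping at the same time: define *misrandomized*, use one consent wording for the Randomized set, and record its narrowing in SAP Section 4.

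The cost is one table cell, at most one sentence and a check of the population flag; no new data are needed. The latest SAP update is dated after database lock, so a change now should be documented as a post-lock clarification with the number of patients whose status changes, even if that number is zero.
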